# **Protocol Body**

# **1.0 Objectives**

1.1 To assess whether the time to progression for these high-risk patients can be prolonged to a median of 36 months, compared to the historical expectation of approximately 24 months.

1.2 To assess the tolerance and efficacy of Y2B8 (Zevalin) after R-FND (rituximab, fludarabine, mitoxantrone, dexamethasone) in patients with high-risk stage III-IV follicular lymphoma

1.3 To assess overall response, failure-free survival, and survival of this strategy compared to our historical experience with FND (fludarabine, mitoxantrone, dexamethasone) alone or R-FND

1.4 To assess the tolerance and efficacy of maintenance therapy with rituximab

1.5 To maximize the 12-month molecular remission rate for patients with high-risk stage III-IV follicular lymphoma

1.6 To correlate the results of quantitative PCR assay with classical PCR and with clinical outcome.

# 2.0 Background

## 2.1 Follicular Lymphoma

Numerous therapies can be effective for patients with follicular lymphoma, but virtually all patients eventually relapse after standard alkylating agent based therapies. Examples of standard therapy are COP (cyclophosphamide, vincristine, and prednisone), CHOP (cyclophosphamide, vincristine, prednisone, and doxorubicin), and FND (fludarabine, mitoxantrone, dexamethasone (1,2)). Increasingly, rituximab is being incorporated into front-line regimens, with promising results (3,4).

Prognostic models can identify subsets who are less likely to attain complete response (CR), or whose remissions are likely to be relatively brief (3, 5-7). A large multi-institutional collaboration has recently led to a prognostic model that identifies high-risk patients based on the presence of 3 or more of the following features: stage III-IV; age 60 or more; elevated LDH; Hgb < 12; and 5 or more involved nodal sites (8).

## 2.2 bcl-2.

The bcl-2 gene is rearranged in about 85% of patients with follicular lymphoma. The small fraction without bcl-2 gene rearrangement appear to have a worse outlook (9). For those with bcl-2 gene rearrangement, the polymerase chain reaction (PCR) provides an excellent way to monitor these patients for subclinical residual disease (10,11). Ultimately, a quantitative PCR technique may prove useful (12); currently, the literature that supports the use of PCR for bcl-2 is based on qualitative (positive or negative) PCR data.

## 2.3 Fludarabine and FND Combination

Fludarabine is an active agent for patients with indolent lymphomas; it has been used in the setting of relapse and up-front, and has been used alone and in combination (13,14). The FND combination has been particularly effective and well tolerated (11-13), and is capable of inducing molecular remission (18).

Our sequential experience with FND started with a phase I trial (15) that has defined a dose that has been adopted widely (16, 19-22). We subsequently conducted a phase II trial in the setting of relapse (17), then front-line trials including one in conjunction with rituximab (6, 23, 24). These latter trials (6, 23, 24) provide the framework for the questions to be addressed in the current trial. The FND front-line experience that has the longest follow-up is DM92-103 (23). Based on that trial, we expect a CR rate of about 80%, and a 5-year failure-free survival of about 40%. The R-FND experience (protocol DM97-261) has shorter follow-up; the DM97-261 experience provides the expectation of a molecular response rate of 80% (17,18).

## 2.4 Rituximab and other monoclonal antibodies

Rituximab is a chimeric anti-CD20 monoclonal antibody (25). As a single agent, it has been effective and well tolerated (26-28). In combination with chemotherapy, it has been well tolerated (24,29). Ongoing trials suggest that rituximab can add to the impact of chemotherapy (30). Rituximab is capable of inducing molecular remissions (31).

Zevalin is a radioimmunoconjugate that targets CD20, the same pan B antigen recognized by rituximab. It is a highly active single agent (32, 33).

The safety profile of Zevalin in five clinical trials revealed that AEs are primarily hematologic with Grade 4 neutropenia, thrombocytopenia, and anemia occurring in 30%, 10%, and 4% of patients, respectively. Most nonhematologic AEs were Grade 1 or 2 and the incidence was comparable to that seen with rituximab. Hematologic toxicity did not correlate with any of the dosimetric or pharmacokinetic parameters analyzed. Patients were effectively screened for safe treatment using clinical selection criteria including percent bone marrow involvement with NHL (<25%), baseline platelet count (> 100,000 cells/mm^3). Patients were treated safely using individualized dosing based on patient weight and platelet count. The incorporation of Zevalin, in sequence with chemotherapy, in the front-line strategy proposed in this protocol is investigational.

# 3.0 Background Drug Information

3.1 Fludarabine is commercially available.

3.2 Mitoxantrone is commercially available.

3.3 Dexamethasone is commercially available.

3.4 Rituximab (Rituxan®) is commercially available. Safety information is as follows:

Hematologic Events: In clinical trials, Grade 3 and 4 cytopenias were reported in 48% of patients treated with rituximab; these include: lymphopenia (40%), neutropenia (6%), leukopenia (4%), anemia (3%), and thrombocytopenia (2%). The median duration of lymphopenia was 14 days (range, 1 to 588 days) and of neutropenia was 13 days (range, 2 to 116 days). A single occurrence of transient aplastic anemia (pure red cell aplasia) and two occurrences of hemolytic anemia following rituximab therapy were reported.

In addition, there have been a limited number of post-marketing reports of prolonged pancytopenia, marrow hypoplasia, and late onset n (defined as occurring 40 days after the last dose of rituximab) in patients with hematologic malignancies. In reported cases of late onset neutropenia (NCI-CTC Grade 3 and 4), the median duration of neutropenia was 10 days (range 3 to 148 days). Documented resolution of the neutropenia was described in approximately one-half of the reported cases; of those with documented recovery, approximately half received growth factor support. In the remaining cases, information on resolution was not provided. More than half of the reported cases of delayed onset neutropenia occurred in patients who had undergone a prior autologous bone marrow transplantation. In an adequately designed, controlled, clinical trial, the reported incidence of NCI-CTC Grade 3 and 4 neutropenia was higher in patients receiving rituximab in combination with fludarabine as compared to those receiving fludarabine alone (76% [39/51] vs.39% [21/53]).

#### 3.4.1 Investigational Drug Nomenclature

- IDEC Pharmaceuticals code designation IDEC C2B8
- Generic Name: Rituximab
- IND Number: BB-IND 4904

#### 3.4.2 Clinical Formulation

Clinical supplies for this study will be manufactured by Genentech Incorporated in South San Francisco, CA.

Rituximab will be provided to the clinical sites packaged in single use 10 mL (100mg) and 50 mL (500mg)Type I glass vials at a concentration of 10 mg of protein per mL. The product is formulated in 7.35 mg/mL sodium citrate buffer, containing 7 mg/mL polysorbate 80, 9.0 mg/mL sodium chloride and Sterile Water for Injection. The pH is adjusted to 6.5.

Rituximab is produced by a mammalian (Chinese Hamster Ovary) cell suspension culture in a nutrient medium containing 100 mg/mL of the antibiotic gentamicin. The antibiotic is not detectable in the final product.

#### 3.4.3 Storage

Rituximab for clinical use should be stored in a secure refrigerator at 2-8 degrees Celsius.

3.4.4 Reconstitution and dilution of rituximab

Using a sterile syringe and a 21 gauge or larger needle, transfer the necessary amount of rituximab from the vial into a partially filled IV pack containing sterile, pyrogen-free 0.9% Sodium Chloride, USP (saline solution). The final concentration of rituximab should be 1 mg/mL. Mix by inverting the bag gently.

Caution should be taken during the preparation of the drug. Parenteral drug products should be inspected visually for particulate matter prior to administration. Preparations of rituximab containing visible particles should not be used. As with all parenteral drug products, aseptic procedures should be used during the preparation and administration of rituximab.

NOTE: DO NOT USE A VACUUM APPARATUS to transfer rituximab from the syringe to the infusion pack. DO NOT USE evacuated glass containers which require vented administration sets, because this causes foaming when air bubbles pass through the solution.

3.5 Zevalin: Zevalin is composed of the following: a murine IgG1 kappa monoclonal antibody IDEC-2B8 (ibritumomab); the linker chelator tiuxetan (isothiocyanatobenzyl MX-DTPA); and the radioisotope Y that is securely chelated via the linker. Like its unlabeled chimeric counterpart, rituximab, Zevalin targets the CD20 antigen present on 95% of B cell lymphomas. IDEC-In2B8 is the Indium-labeled murine monoclonal antibody used for imaging and dosimetry. Rituximab is given initially to clear peripheral B lymphocytes and optimize biodistribution of the radiolabeled antibody. Dosimetry studies have shown that normal organ and red marrow radiation doses were estimated to be well under 2000 cGy and 300 cGy, respectively. Estimated median tumor absorbed dose as determined by data from 18 tumors in 9 patients was 1712 cGy (range 575 – 6710). In a specific analysis of safety, estimated absorbed red marrow radiation dose (performed by blood-derived and sacral image-derived methods), blood T1/2, blood AUC, plasma T1/2, and plasma AUC did not predict severity of hematologic toxicity as demonstrated by the lack of clear correlation between these variables. In a multicenter phase II trial, adverse events were primarily hematologic, transient, and reversible. The median nadirs were 34,000/mm^3 for platelets, 60/mm^3 for ANC, and 10.0 g/dL for hemoglobin. Grade 4 neutropenia and thrombocytopenia occurred in 31% and 12% of patients.

## 3.5.1 Investigational Drug Nomenclature

- IDEC Pharmaceuticals code designation: Zevalin (IDEC-106); IDEC-2B8-MX-DPTA (IDEC-129)
- Generic name: Y-Ibritumomab tiuxetan
- IND numbers: BB-IND 4850 Zevalin
- MF number: BB-MF 7087 Zevalin
  - 3.5.2 Clinical Formulation

The radiolabeling kit is provided by IDEC and all components are tested to be sterile and pyrogen-free. The kit consists of the following components:

- 3 mL glass vial containing 2 mL (3.2 mg) of Zevalin at 1.6 mg/mL in low metal normal saline
- 3 mL glass vial containing 2 mL low-metal 50 mM sodium acetate
- 10 mL glass vial containing 10 mL formulation buffer (PBS containing 7.5% human serum albumin and 1 mM DTPA, pH 7.2)
- 10 mL glass vial (empty)
- 3.5.3 Storage

The radiolabeling kits should be stored in a secure refrigerator at 2-8 degrees Celsius. Zevalin solutions are stable at 2-8 degrees Celsius for up to 8 hours following preparation. Due to the relatively short half life of the 90Y isotope, if not used soon after calibration time, the actual dose will have decayed and will require recalculation.

# 4.0 Patient Eligibility

4.1 Patients with previously untreated Ann Arbor stage III-IV follicular lymphoma, grade 1 and 2, with high-risk features are eligible for this protocol. High-risk is defined according to the FL-IPI (4), based on the presence of advanced stage, plus any additional 2 of the following 4 features: age 60 or more; elevated LDH; Hgb < 12; or number of involved nodal sites 5 or more.

4.2 Follicular lymphoma, grade 3 (follicular large cell lymphoma): If eligible for a current large cell lymphoma protocol, that alternative protocol is recommended, particularly grade 3b or FLCL patients characterized as large non-cleaved cell. However, both FND and rituximab have established efficacy in FLCL, so if a patient is not eligible for a protocol for aggressive lymphoma (e.g., because of SCCL in the marrow), then registration on this trial is permitted.

4.3 Biopsy or FNA material is strongly recommended for bcl-2 studies to verify rearrangement status of all patients who are designated "germline" (see section 6.4). For other patients, tissue availability is desirable but not mandatory.

4.4 No age limit. Any pediatric candidate (age <16) will be discussed with Pediatrics.

4.5 Women must not be pregnant.

4.6 Patients must have a performance status of Zubrod 3 or better (Appendix H).

4.7 Patients must have adequate renal and hepatic function (creatinine < 2mg%; bilirubin < 2 mg%). Patients with renal or liver dysfunction due to organ infiltration by lymphoma may be eligible after discussion with the study chairman.

4.8. Patients may not receive other concurrent chemotherapy, radiotherapy, or immunotherapy.

4.9 Patients must sign an informed consent indicating that they are aware of the investigational nature of this study in keeping with the policies of the hospital.

4.10 Exclusions:

4.10.1 Patients who are unable or unlikely to be able to adhere to the treatment plan or to return to Houston for follow-up visits because of geographical, economic, emotional, or social considerations are not eligible for this study. Note: some follow-up care may be provided by outside physicians as long as the MDACC protocol for outside physician participation is strictly adhered to (see Appendix G).

4.10.2 Patients with an absolute peripheral granulocyte count of < 1,000 and platelet count < 100,000 unless due to marrow infiltration or hypersplenism.

4.10.3 Patients with organ dysfunction, including bilirubin of > 2 mg% or serum creatinine level > 2 mg%, unless the alteration is due to lymphoma.

4.10.4 Patients with HIV infection should not be registered on this protocol.

4.10.5 Patients with an antecedent malignancy whose prognosis is poor (< 90% probability of surviving for 5 yrs).

4.10.6 All patients should have a cardiac ejection fraction of 50% or more by echocardiography or MUGA.

4.10.7 Patients who will not accept transfusions of blood products or supportive care measures such as antibiotics are not eligible for this study.

4.10.8 Female patients must not be pregnant or lactating, and men and women of reproductive potential must follow accepted birth control methods.

4.10.9 Patients who have received prior murine antibody therapy will be excluded.

4.10.10 Patients with evidence of active or prior infection of Hepatitis B are excluded. (Note: Persons vaccinated for Hepatitis B who have + antibodies are not excluded).

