5.1 R-FND

5.1.1 Initial Dose Regimen of R-FND - Course 1: please note that there are 2 doses of rituximab for course 1 only:

AGENT	DOSE	DAY	ROUTE	TIME
Fludarabine	25 mg/m²/day	2-4	I.V.	5-30 minutes
Mitoxantrone	10 mg/m 	2	I.V.	5-30 minutes
Dexamethasone	20 mg/day	2-6	PO or I.V.	
Rituximab*	375 mg/m²/dose	1* & 8	I.V.	4-6 hours

\*For leukemic patients, because of the risk of lysis, rituximab Day 1 dose will be deferred to Day 3 (or later at clinician's discretion). Missed rituximab doses will be made up in subsequent courses; discuss with P.I.

Subsequent Monthly Dose Regimen of R-FND – Courses 2 and beyond: please note that there is only 1 dose of rituximab:

AGENT	DOSE	DAY	ROUTE	TIME
Fludarabine	25 mg/m²/day	1-3	I.V.	5-30 minutes
Mitoxantrone	10 mg/m 	1	I.V.	5-30 minutes
Dexamethasone	20 mg/day	1-5	PO or I.V.	
Rituximab	375 mg/m 	1	I.V.	4-6 hours

5.1.2 Rituximab is recommended to start two hours before fludarabine. Mitoxantrone is recommended to be given after the first dose of fludarabine. Courses are recommended to be repeated each four weeks, after documentation of recovery from the prior course, including platelets > 100,000, and granulocytes > 1500.

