5.1.3 Dose Levels

	-2	-1	0
Fludarabine	16 x 3	20 x 3	25 x 3
Mitoxantrone	6	8	10

Dose Reduction of rituximab is discouraged, but may be discussed with the P.I.

5.1.4 Patients are recommended to receive fludarabine phosphate I.V. over 5-30 minutes daily for 3 days. Mitoxantrone is recommended to be given I.V. over 5-30 minutes. Rituximab will be given as in section 5.1. Courses are recommended to be repeated every 4 weeks. Restaging on R-FND is recommended to be conducted after completion of 2 and 4 courses.

5.1.5 Patients achieving a stable partial response or demonstrating continued response after 4 courses may be given an additional 2 courses. Discuss with P.I.

5.1.6 Patients demonstrating progressive disease or no response after 2-4 courses will come off study. See section 9.1.

5.1.7 Dose adjustment to the next lower level will be made if pneumonia, septicemia, or other life-threatening infection occurs with any course. If recovery of the WBC or platelet count to the level prior to treatment exceeds 35 days, the dose may be decreased 1 level. If grade 3 or 4 toxicities to other organ systems develops, the dose level may be lowered 1 or 2 levels respectively.

5.1.8 Four courses is the intended limit for R-FND. For patients with substantial (>20%) ongoing shrinkage of measurable disease between courses 2 and 4 will receive additional R-FND, if their hematologic tolerance has been good. If such special circumstances warrant consideration of additional R-FND, please discuss with P.I.

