5.4 Zevalin Radioimmunotherapy (see Appendices I and J)

Candidate patients: PR or CR after R-FND x 4 5.4.1

5.4.2 Exclusions:

- persistent marrow infiltrate > 25% -- n.b., most such patients will not meet PR criteria anyway. ٠
- Hypocellular bone marrow (cellularity less than 15%) •
- Marked reduction in bone marrow precursors of one or more cell lines (granulocytic, megakaryocytic, erythroid)
- Platelet count <100.000/mm^3 ٠
- creatinine, bilirubin, AST/ALT or alkaline phosphatase > 2 x the upper limit of normal.
- Active infection
- pleural effusion

- G-CSF or GM-CSF within 2 weeks
- Performance status 3 or more

5.4.3 Schedule: Zevalin to start approximately 12-16 weeks after last course of R-FND, pending hematologic recovery as outlined above in 5.4.2

5.4.3.1 The Y isotope order form must be completed and faxed to the designated isotope vendor preceding the initial rituximab infusion. Patients will receive an initial infusion of 250 mg/m^2 rituximab. One week later, patients must receive a second infusion of 250 mg/m^2 of rituximab and 0.3 mCi/kg of ZEVALIN. The exact dose of ZEVALIN will be based on the patient's weight during the baseline evaluation. The maximum dose is not to exceed 32 mCi of Y.

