5.6. Chemotherapy Dose Modification Guidelines

5.6.1 Recommended Guidelines for Hematological Toxicity: for fludarabine and mitoxantrone (see 5.1.3):

Lowest granulocytes	Lowest Platelets	Modification		
>200	> 20,000	No change		
<200 for > 5 days and/or	< 20,000	Decrease one level		
documented infection with neutropenia	Bleeding	Decrease one level		

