# 6.0 Pretreatment evaluation (see Appendix E)

6.1 A complete history and physical, including documentation of performance status, all measurable disease, screening for active or prior hepatitis B, as well as signs and symptoms shall be necessary.

6.2 Laboratory studies:

6.2.1 Mandatory (within 30 days of study entry): CBC, differential, and platelet count, chemical survey. Women of child-bearing potential will have a pregnancy test (serum HCG).

6.2.2 Recommended: Beta-2 microglobulin, quantitative immunoglobulins, serum protein electrophoresis, and immunofixation if monoclonal peak is identified. Plasma for soluble CD20 if possible.

6.3 Bone marrow aspirate and biopsy (bilateral biopsy; unilateral aspirate).

6.3.1 Marrow cytogenetics recommended. For exceptions, discuss with PI.

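### Exclusion 4.10.2 joins its two low-count limits with 'and', so read literally a single unexplained low count does not bar entry or full-dose course 1 of R-FND

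*Combined protocol and SAP*

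**What the plan says.** Section 4.10.2 lists this exclusion: "Patients with an absolute peripheral granulocyte count of < 1,000 and platelet count < 100,000 unless due to marrow infiltration or hypersplenism".

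Other places in the protocol that set or use blood counts or paired laboratory limits:

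- **4.7** states the renal and hepatic limits as an entry requirement (creatinine and bilirubin each below 2 mg%). It sets no minimum blood count.
- **4.10.3** restates those limits as an exclusion for organ dysfunction, including "bilirubin of > 2 mg% or serum creatinine level > 2 mg%, unless the alteration is due to lymphoma".
- **6.2.1** requires the baseline counts but attaches no limit: "Mandatory (within 30 days of study entry): CBC, differential, and platelet count, chemical survey".
- **5.1.1 and 5.1.3** start R-FND at dose level 0: fludarabine 25 mg/m² for 3 days and mitoxantrone 10 mg/m². **5.6.4** gives patients over 60 full doses as well.
- **5.1.2** recommends repeating courses every four weeks, "after documentation of recovery from the prior course, including platelets > 100,000, and granulocytes > 1500".
- **5.4.2** bars the later Zevalin step on platelets alone: "Platelet count <100.000/mm".
- **5.6.3(b)** allows R-FND to stop early for cumulative myelosuppression when recovery of granulocytes to 1000 or of platelets to 100,000 takes more than 6 weeks. The two limits are joined by 'or'.

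**The concern.** An exclusion that joins two conditions with 'and' applies only when both are met. Put the other way round, the literal text of 4.10.2 lets a patient in when either count is adequate. A count floor before myelosuppressive chemotherapy would normally require both to be adequate.

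What is at stake is safety at entry and during course 1. Because 4.10.2 is the only count limit found ahead of that course, its one connecting word carries the whole rule. Under the literal reading a patient with one severe unexplained cytopenia can be registered without a deviation. Under the other reading the same patient is ineligible. Two investigators could apply the sentence differently and each believe they had complied.

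**Working it through.** No figure in the plan is at issue, so the check is one of logic and of cross-reading.

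**Step 1. The rule in both forms.** Let G be 'granulocytes below 1,000', P be 'platelets below 100,000', and E be 'due to marrow infiltration or hypersplenism'.

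- As written, read literally: excluded if (G and P) and not E.
- With 'or': excluded if (G or P) and not E.

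**Step 2. All cases with at least one low count.** There are 3 count patterns, each with or without the exception, so 3 × 2 = 6 cases. The counts shown are examples.

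| Granulocytes | Platelets | Exception applies | Excluded, literal 'and' | Excluded, 'or' |
|---|---|---|---|---|
| 400 | 40,000 | no | yes | yes |
| 400 | 200,000 | no | **no** | **yes** |
| 3,000 | 40,000 | no | **no** | **yes** |
| 400 | 40,000 | yes | no | no |
| 400 | 200,000 | yes | no | no |
| 3,000 | 40,000 | yes | no | no |

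Literal 'and' excludes 1 of 6 and 'or' excludes 3 of 6, so 3 − 1 = 2 cases change. Both are a single low count without the exception. These are logical cases, not patients, and say nothing about frequency.

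**Step 3. Does anything else set a count floor before course 1?**

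- 4.7 and 4.10.3 cover renal and hepatic function only.
- 6.2.1 asks for the measurement without a limit.
- 5.1.2 concerns recovery from a preceding course, so it governs course 2 onward.
- 5.4.2 governs Zevalin only.
- The dose rules act after a course has been given: 5.1.7 ("Dose adjustment to the next lower level will be made if pneumonia, septicemia, or other life-threatening infection occurs with any course"), 5.6.1 (low nadirs, bleeding, "documented infection with neutropenia") and 5.6.5 (slow granulocyte recovery or neutropenic fever).

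None closes the gap. Sections 5.0 and 6.0 refer to Appendices D and E, which were not available, so this finding covers the protocol body only.

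**Step 4. Which meaning was probably intended?**

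- 5.6.3(b) uses the same two numbers, 1000 and 100,000, with 'or'. Its natural reading is that delay in either count is enough to act on.
- 4.10.3, the next exclusion, also pairs two laboratory limits with an exception for disease-related causes, and uses 'or'. Section 4.7 confirms that meaning by stating the same limits as requirements. Nothing in Section 4 does the same for 4.10.2.

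Both point to 'or'. They are evidence of intent, not proof.

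**The case against.** The strongest reply is that this is an ambiguity that any clinician would resolve correctly. In an exclusion list, naming patients with one feature and another can mean two groups, each excluded. The list is not drafted for strict parsing in any case: 4.10.6 (ejection fraction) and 4.10.8 (pregnancy and contraception) sit under exclusions but are worded as requirements. That stands, and the distributive reading is probably the intended one. It does not remove the need for the change, because the sentence does not say so and a strict reader would not be in breach.

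The evidence of intent also has limits. Section 4.10.3 works through an umbrella term, organ dysfunction, which 4.10.2 lacks. A drafter who used 'or' elsewhere could have chosen 'and' deliberately here. The platelet bar in 5.4.2 belongs to a radioimmunotherapy step with its own marrow criteria and says little about entry to chemotherapy.

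Other protections exist around course 1: weekly counts are recommended (7.1), safety is reviewed after 10 enrolments (10.4), and two treatment-related deaths put the study on hold (10.2). None is an entry threshold.

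Two stronger inferences are tempting, and the documents do not support them:

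- A reader might take the grade 3–4 neutropenia rates in Section 3.4 (39/51 with rituximab plus fludarabine, 21/53 with fludarabine alone) as showing the harm of a low starting count. They compare regimens and contain nothing about baseline counts.
- A reader might argue that a patient who would fail the 5.1.2 counts has been wrongly admitted. Section 5.1.2 is a recommendation about recovery from treatment and asks for granulocytes above 1500. A patient with granulocytes of 1,200 and adequate platelets would enter even under 'or' and still fail it.

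**Conclusion.** The point holds as a defect of wording in an operative safety rule. Followed literally, 4.10.2 admits a patient with one low count from a cause outside the exception to full-dose course 1, and nothing else in the supplied body prevents it. The protocol does not show that its authors wanted this, or that any such patient would be treated; the likelier intent is that either low count excludes.

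The effect is confined to the two cases identified above. The number of patients cannot be derived from the documents. It is assumed to be small, because patients are previously untreated and those with HIV or hepatitis B infection are excluded. The conclusion also assumes that no unseen appendix sets a count floor before course 1; if one does, 4.10.2 should still be made to agree with it.

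The maximum of 50 patients, the 0.03 stopping cutoff and the simulated operating characteristics in Sections 10.1, 10.4 and 10.5 are unaffected.

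**What to change.** In 4.10.2, replace the 'and' between the granulocyte and platelet limits with 'or', so that either low count excludes. Keep the exception for marrow infiltration or hypersplenism as it stands, so that patients whose low counts come from those causes remain eligible.

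This is a one-word amendment. Its only downside is a slightly smaller eligible pool. No sample size, stopping rule or analysis needs to be revised.
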